9.1.2 Symptomatic Influenza Infection

Modified Jackson Instrument score. ([Appendix C](#)) Symptomatic influenza infection for determining AR will be assessed using a Modified Jackson score collected by study staff twice a day (approximately 8 AM and after 3 PM) from the time of admission until the time of discharge. The Modified Jackson score will be calculated after evaluation of vital signs, laboratory results, and the Modified Jackson score across multiple days.

FluPro® participant reported tool. ([Appendix B](#)) A previously validated, patient-reported outcome (PRO) measure to standardize the assessment of influenza symptoms in clinical research (i.e., FLU-PRO Survey Instrument and Validation Diary) will be completed by subjects once a day (after 3:00 PM) from the time of admission through discharge. The investigators will review the FLU-PRO and Validation Diary responses each day.

Fever. A febrile illness, with or without accompanying symptoms, will be defined as an occurrence of an oral temperature of $\geq 100.2^{\circ}\text{F}$ ($\geq 37.9^{\circ}\text{C}$). *Note: a qualifying temperature of $100.2^{\circ}\text{F}-100.5^{\circ}\text{F}$ does not constitute a gradable toxicity (see [Appendix A](#)).* Elevated temperatures must be confirmed with a repeat measurement within 5-60 minutes.

Clinical Findings of Respiratory Tract Infection. At least once daily, the study physician will perform at least a limited physical examination of the head, neck, and lungs; a directed or more detailed physical examination may be performed at the discretion of the study physician for any reason. Physical examination findings which would be consistent with an influenza infection will include:

- Nasal discharge
- Otitis
- Sinus tenderness
- Pharyngitis
- New wheeze, rales, rhonchi, or other lower tract signs

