6.9 Discharge Criteria

Subject discharge is planned at approximately 14 days (for Recipient participants) or 2-5 days (for Donor participants) after entry. To be eligible for discharge home, the participant must meet the following criteria: no greater than moderate severity influenza signs or symptoms (Appendix A) and are clinically stable during their stay. In addition, the participant must attest that they feel well enough to provide their own self-care. Otherwise, Recipients will be discharged as described in escalation of care (Section 6.8). Recipients must be at least 2 days post the end of their last exposure event to be eligible for discharge. We may discharge Recipients with a home influenza test to ensure that we do not miss late onset, long latency, influenza infection. However, recipients who have contracted the flu but do not wish to be a donor may be discharged earlier. In this case, they must meet the discharge criteria described above for discharge home. All other instances will be handled as described in Section 6.8.

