7.2 Adverse Events and Serious Adverse Events

Definition of Adverse Events (AE)

ICH E6 defines an AE as any untoward medical occurrence in a patient or clinical investigation subject administered a pharmaceutical intervention regardless of its causal relationship to the study treatment. FDA defines an AE as any untoward medical occurrence associated with the use of a drug in humans, whether or not considered drug-related (21 CFR 312.32 (a)).

An AE can therefore be any unfavorable and unintended sign (including an abnormal laboratory finding), symptom, or disease temporally associated with the use of medicinal (investigational) intervention. The

occurrence of an AE may come to the attention of study personnel during study visits and interviews of a study recipient presenting for medical care, or upon review by a study monitor.

In this study, solicited symptoms of symptomatic influenza infection will be collected from the time of first exposure event through 7 days post-last-exposure and will **not** be considered adverse events. Objective clinical examination findings consistent with the solicited symptom, such as oropharyngeal erythema or lymphadenopathy, will also **not** be considered AEs. Any influenza signs, symptoms or lab findings determined by the clinician to have exceeded the expected severity or any moderate or severe complications, as listed in [Section 2.5.1](#), will be considered unsolicited adverse events and captured on the appropriate data collection form and electronic case report form (eCRF). Events that are not consistent with illness due to influenza will be considered unsolicited AEs as well. Events that occur after administration of antivirals will also be considered unsolicited AEs. Any chronic or stable medical condition that is present at the time that the subject is screened will be considered as baseline and not reported as an AE. However, if the severity of any pre-existing medical condition increases, it should be recorded as an AE.

Classification of an Adverse Event

The determination of seriousness, severity, and causality will be made by an on-site investigator who is qualified (licensed) to diagnose AE information, provide a medical evaluation of AEs, and classify AEs based upon medical judgment. This includes but is not limited to physicians, physician assistants, and nurse practitioners.

Definition of Serious Adverse Events

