AEs characterized as intermittent require documentation of onset and duration of each episode. The start and stop date of each reported AE will be recorded on the appropriate data collection form and eCRF. Changes in the severity of an AE will be documented to allow an assessment of the duration of the event at each level of intensity.

Relationship to Study Intervention

The licensed study clinician's assessment of an AE's relationship to study intervention is part of the documentation process, but it is not a factor in determining what is or is not reported in this study. If there is any doubt as to whether a clinical observation is an AE, the event should be reported. The relationship to study intervention must be assessed for AEs using the terms: related or not related.

- **Related** – The AE is known to occur with the study intervention, there is a reasonable possibility that the study intervention caused the AE, or there is a temporal relationship between the study intervention and event. Reasonable possibility means that there is evidence to suggest a causal relationship between the study intervention and the AE.
- **Not Related** – There is not a reasonable possibility that the administration of the study intervention caused the event, there is no temporal relationship between the study intervention and event onset, or an alternate etiology has been established.

Time Period and Frequency for Event Assessment and Follow-Up

In this study, solicited symptoms of influenza infection will be collected from the time of first exposure event through 7 days post-last-exposure and will **not** be considered adverse events. Unsolicited AEs will be captured starting at the time of exposure through 28 days post-exposure. AEs will be followed through resolution. Resolution of an AE is defined as the return to pretreatment status or stabilization of the condition with the expectation that it will remain chronic.

Adverse Event Reporting

Investigators Reporting of AEs

Information on all AEs should be recorded on the eCRF. Information to be collected for AEs includes event description, date of onset, assessment of severity, relationship to study intervention and alternate

etiology (assessed only the site Principal Investigator or Co-investigator with the training and authority to make a diagnosis), date of resolution, seriousness, and outcome. AEs occurring during the study will be documented appropriately regardless of relationship.

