17 APPENDIX D: SCHEDULE OF EVENTS

Recipients Participating in a CHIVITT Cohort

Inform of upcoming CHIVITT, ~1 wk prior
 Sign Recipient CHIVITT Consent Form
 Vital signs (SpO₂, HR, RR BP, temp)
 Targeted physical exam
 Nasal Swab, resp virus panel
 Nasal Swab, viral quantification
 Saliva Sample, viral quantification
 Nasal Wash, ~5-10 mL
 Point of care urine pregnancy for FOCBP
 Research Blood, ~10 mL
 Clinical Safety Lab Blood, ~10 mL
 Modified Jackson Score, twice daily
 FLU-PRO survey⁷, once daily
Exposure Events
 Exhaled Breath Sampling
 12-lead electrocardiogram
 Influenza Therapy (anti-viral)
 Adverse Event Reporting

CHIVITT – approx. 14 days on Quarantine Research Unit (w/in 48h) (w/in 72h)								Outpt Clinic Follow-Up ~1 month	Phone Call Follow-Up ~2 months
Pre-Adm	Admission	Daily*	Intermittent or Additional	upon influenza infection	(as requested) Ad Hoc	Discharge, ~Day 14			
X									
	X								
	X	X ¹			X	X ³			
	X	X				X			
	X	X ²	X			X ³			
	X	X ²	X			X ³			
	X	X ²	X			X ³			
	X						X		
	X								
	X		X			X ⁴	X		
				X ⁵	X ⁶				
		X							
		X				X9			
			X						
			X						
				X8					
	X	X	X	X	X	X	X	X	X

* – Daily including Day 1 unless completed as part of admission procedures.

1 – routine daily vital signs are to be performed twice daily (morning and afternoon), except once a day if the Recipient has been observed on the unit for more than two days and has not been exposed to a Donor.

2 – routine daily swabs and saliva may not be necessary prior to first exposure to a Donor and after the first two days of negative tests.

3 – to be performed/collected if not done within the past 12 hours

4 – to be collected if not done within the past 48 hours

5 – these clinical safety labs include: WBC, ALC, Hgb, PLT, ALT, and Cr

6 – these clinical safety labs are to be determined by the requesting clinician; may include: chemistry, hematology, coagulation, cardiac enzymes, and urinalysis

7 – the FLU-PRO survey is completed by the participant

8- Unless consenting to continue in the CHIVITT as a Donor

9 – the FLU-PRO survey won't be administered at discharge if the discharge occurs before 3pm, as the survey becomes available at 3pm.

Donors Participating in a CHIVITT Cohort

Identification of potential influenza case
 Lab-confirmation influenza infection, w/in 48h
 $F \geq 100.2^{\circ}\text{F}$ AND cough or sore throat, w/in 48h
 Sign Donor CHIVITT Informed Consent Form
 Vital signs (SpO₂, HR, RR BP, temp)
 Targeted physical exam

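### Solicited symptoms are to be collected through 7 days after last exposure, but both symptom instruments stop at discharge, so graded illness severity is truncated for Recipients who leave sooner

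*Protocol*

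**What the plan says.** **Collection window.** Protocol section 7.2 states it twice. Under the definition of adverse events: "solicited symptoms of symptomatic influenza infection will be collected from the time of first exposure event through 7 days post-last-exposure". Under the time period for event assessment: "solicited symptoms of influenza infection will be collected from the time of first exposure event through 7 days post-last-exposure". Both sentences add that these symptoms are not adverse events. Section 7.1 likewise excludes mild and moderate influenza signs and symptoms from adverse events for 7 days after illness onset.

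**Instruments.** Section 9.1.2 names two. The Modified Jackson score, which is used to assess symptomatic infection for the attack rate, is collected by staff "twice a day (approximately 8 AM and after 3 PM) from the time of admission until the time of discharge". FLU-PRO "will be completed by subjects once a day (after 3:00 PM) from the time of admission through discharge". In Appendix D both sit in the daily column of the stay, with FLU-PRO also at discharge. A footnote there adds that "the FLU-PRO survey won't be administered at discharge if the discharge occurs before 3pm". The next scheduled contact is the 1-month clinic visit.

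**Discharge.** Section 6.9: "Recipients must be at least 2 days post the end of their last exposure event to be eligible for discharge". Section 2.5.1 gives about three days of observation after last exposure. Section 6.9 also says that "recipients who have contracted the flu but do not wish to be a donor may be discharged earlier".

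**Endpoints.** Section 9.1 defines the secondary attack rate (SAR) by virological, symptomatic or serological evidence. Section 5 lists disease severity in Donors and Recipients as a secondary endpoint.

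**The concern.** Section 7.2 promises symptom data for a week after last exposure, but 9.1.2 and Appendix D provide no means of collecting them once a Recipient has gone home. The adverse-event rules make this worse. Mild and moderate influenza symptoms are kept out of adverse-event reporting because they are meant to be captured as solicited symptoms. After discharge nothing captures them in that form, so as a rule they fall outside both systems.

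What is at stake is mainly the severity endpoint. Daily scores end when the stay ends, and length of stay is partly the participant's choice. An infected Recipient who consents to become a Donor may remain for up to 5 days in that role (section 6.6), with daily scoring. One who declines may leave. Recorded severity then depends partly on when the person left. FLU-PRO asks about the preceding 24 hours (Appendix B), so the 1-month visit cannot rebuild the missing days.

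A smaller matter is the symptomatic component of the SAR, for illness that begins after discharge.

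**Working it through.** The plan gives no figure for this point, so the check is of the collection windows.

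**Inputs (all from the Protocol)**
- Stated symptom window: 7 days after last exposure (7.2).
- End of both instruments: discharge (9.1.2, Appendix D).
- Earliest routine discharge: 2 days after last exposure (6.9); about 3 days by the account in 2.5.1.
- Run-in: 2 days; exposure events spread over up to 9 or 10 days (6.1).
- Planned discharge: about day 14 (6.9).

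**Step 1. Days of the stated window without an instrument**

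Uncovered days = max(0, 7 − days from last exposure to discharge).

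| Discharge, days after last exposure | Uncovered days | Share of 7 |
|---|---|---|
| 0 (infected, leaves early) | 7 | 100% |
| 1 (infected, leaves early) | 6 | 86% |
| 2 (routine minimum) | 5 | 71% |
| 3 (as in 2.5.1) | 4 | 57% |
| 7 or more | 0 | 0% |

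**Step 2. Does the protocol's own timetable produce the gap?**

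Last exposure day = 2 + exposure span. Days observed afterwards = 14 − last exposure day.

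| Exposure span (days) | Last exposure day | Days observed | Uncovered days |
|---|---|---|---|
| 10 | 2 + 10 = 12 | 14 − 12 = 2 | 7 − 2 = 5 |
| 9 | 2 + 9 = 11 | 14 − 11 = 3 | 7 − 3 = 4 |
| 7 | 2 + 7 = 9 | 14 − 9 = 5 | 7 − 5 = 2 |
| 4 | 2 + 4 = 6 | 14 − 6 = 8 | 0 |

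The 9- and 10-day spans are those named in 6.1; the 7- and 4-day rows are illustrative. The gap appears when exposure runs late in the stay or discharge is early. It does not arise for every Recipient.

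**Step 3. What else could record symptoms between discharge and day 7?**
- Section 6.6: infected participants are intended to be followed to resolution, possibly by telephone, with resolution dates documented. This can give duration but not daily graded scores.
- Section 6.9: a home influenza test may be supplied. This can detect infection but carries no symptom instrument.
- Section 8.1.8: at about 1 month, questions on recovery and unscheduled medical visits, plus blood for serology. This bears on infection status but not on daily severity.

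None of these continues either instrument past discharge.

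**The case against.** The strongest reply is that the 7-day sentence belongs to the safety section. Its job there is to say which symptoms are not adverse events, and it names neither instrument. Section 9.1.2 sets its own window, and Appendix D matches it. That is fair as far as it goes: the endpoint definition does not contradict itself. But 7.2 says that symptoms will be collected in that window, not only how they will be classified, and no other section says how.

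Three stronger readings are tempting and are not supported.

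- *Late-onset infections are lost to the primary endpoint.* The SAR can be met by any one of three kinds of evidence. Serology at about 1 month counts (9.1.3), and the optional home test is aimed at late infection. Infected Recipients who leave early have already been counted. The 24 to 48 hour incubation period given in 2.5.1 also suggests that most onsets precede discharge. Only a case meeting the symptomatic component alone would be missed, and the documents give no basis for estimating how many there are.
- *The illness course of early leavers is wholly unobserved.* Section 6.6 intends follow-up to resolution with dates. Symptoms beyond the expected severity are reportable as adverse events, and 7.2 also treats events after antiviral administration as unsolicited adverse events, which may bring in some symptoms of treated Recipients. Neither route is a daily graded score.
- *Five of seven days (71%) are missing in general.* That figure holds only at the 2-day minimum.

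Nor do the documents show a difference between the randomised groups. The truncation follows length of stay and the decision to become a Donor. Those who become Donors and those who leave also differ in antiviral treatment (6.6), so longer scoring alone would not make them comparable.

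**Conclusion.** The point holds as a conflict between section 7.2 on one side and section 9.1.2 with Appendix D on the other. For Recipients discharged less than 7 days after last exposure, part of the stated window has no symptom instrument: up to 5 of 7 days at the routine minimum, 4 of 7 at about three days, more for an infected Recipient who leaves sooner, and none from seven days on. Mild or moderate symptoms in that gap are not scored and, under the general rule, not recorded as adverse events.

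The main consequence is for the secondary severity endpoint, where daily scores are truncated by length of stay although resolution dates may be available. The effect on the primary SAR is confined to cases that only the symptomatic component would identify. The timetable figures assume a 2-day run-in and discharge on day 14, both taken from the Protocol. This should be corrected, because scores that were never collected cannot be recovered in the analysis. The timing of discharge and treatment are not judged here.

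**What to change.** Have Recipients complete the same FLU-PRO survey remotely once a day from discharge through day 7 after last exposure, or through resolution if infected. Write this into 9.1.2 and add a column to Appendix D, so that both agree with 7.2. Use the data for the severity endpoint and to document late-onset symptoms. Do not use them in place of the Modified Jackson score in the attack-rate definition, since that score is staff-collected and read with vital signs and laboratory results that a remote survey does not supply.

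The cost is small, because the survey is already self-completed: a few more days of entries per Recipient. Some entries will be missing, and some symptoms will come from illness caught in the community during peak season, so post-discharge symptoms without confirmation of influenza should be labelled as such. If the sponsor does not want collection after discharge, the window in 7.2 should be amended to match the schedule, and the protocol should state how mild and moderate symptoms after discharge are recorded.

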9.1.3 Serological Confirmation of Influenza Infection

Seroconversion. A positive seroconversion will be defined as achieving ≥ 4 -fold increase in serum HAI titer from baseline. The serological assessment will be performed in batched analyses and will not be available for day-to-day decisions.

Seropositive. A seropositive will be defined as a serum HAI titer of ≥ 40 at 1-month post-CHIVITT. The serological assessment will be performed in batched analyses and will not be available for day-to-day decisions.

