6 CHIVITT STUDY DESIGN

Each CHIVITT is planned to be conducted with discrete cohorts of Recipients and Donors. The size of each cohort and numbers of Recipients and Donors will vary from cohort to cohort, but the general size of a cohort may consist of up to 20 Recipients and up to 5 Donors per CHIVITT, which would span an approximate 2-week period. The number of Recipients will be determined by each individual's availability and whether their most recent serum antibodies have demonstrated a relative low titer against the influenza virus to be transmitted in the CHIVITT. To maintain the size of the recipient group, we may consider bringing in new recipients during the quarantine study if a significant number of original recipients are infected on the same day. The number of Donors will be determined by the number of participants which are identified with acute symptomatic influenza infection during the time of a CHIVITT cohort's stay.

The CHIVITT studies are anticipated to occur during the peak of local seasonal influenza transmission (e.g., January and February). Timing of the study will be constrained by the necessity to rent the facility for prespecified calendar dates. It is intended that the local seasonal influenza activity will be closely monitored, including the virus subtypes which are predominantly circulating. During the peak of the local seasonal influenza activity, a cohort of Recipients will be contacted to request their willingness to reside up to ~2 weeks on the quarantine research unit for a CHIVITT. The selection of Recipients from the pool of potential Recipients will be partially determined by the demonstration of low antibody titers against the circulating influenza virus, which has been measured in the past year (under the EMIT-2 Recipient Protocol, UMB IRB HP-97730). Potential Recipients will be given some time (\leq one week) to decide whether to participate and they must complete an IRB-approved consent form for the CHIVITT study.

Meanwhile, during the peak of community-wide local seasonal influenza the study team will be attempting to rapidly identify healthy adults with acute and symptomatic influenza infection for consent to participate as Donors in the CHIVITT cohort. It is intended that there could be multiple Donors identified during a ~2-week period; each of these Donor individuals could be introduced into the CHIVITT cohort in an overlapping or sequential fashion, to provide more opportunities for transmission events.

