8 CHIVITT STUDY PROCEDURES/EVALUATIONS

8.1 Study Procedures

8.1.1 Admission/entry to a CHIVITT cohort

- Obtaining of informed consent or confirmation of signed informed consent
- Vital signs (including SpO₂, HR, RR, BP, and oral temperature) and height and weight will be obtained
- A targeted physical examination may be performed, as directed by the medical history, medications, and vital signs assessment. An absence of significant past medical history, concomitant prescription medications, and abnormalities in vital signs will not require a physical examination.
- Review and record medical history* and concomitant medications†.
 - *All significant past and current diagnoses will be documented. All signs and symptoms (regardless of severity) that the subject has experienced within 30 days prior to screening will be documented. Medication allergies will also be documented on this form.
 - †All prescription and non-prescription medications, alternative therapies, and vaccines taken within 90 days prior to screening or since the last study visit should be documented.
- For Donors and Recipients, performance of a multiplex influenza, SARS-CoV-2, respiratory virus panel test (e.g., BioFire Respiratory Virus panel)
- For Donors, collection of a respiratory sample for viral quantitation
- Venous whole blood (~10 mL) collection for HAI and FRNT assays and the storage of remaining volumes for secondary research
- For Recipients only, Nasal wash specimen (~5-10 mL) will be collected.
- Additional nasal swab and a saliva sample for research tests (Participants will be asked to collect a saliva sample using a standard protocol and by spitting into a screw cap specimen cup or 50 mL polypropylene screw cap tube).
- For Donors, Exhaled breath sampling within 24 hours of entry.
- Point of care urine pregnancy test for donor and recipient females of childbearing potential within 24 hours of admission to the hotel quarantine unit (to be completed prior to any exposure events)

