8.1.8 Outpatient Clinic Follow-up Visit (~1 month from CHIVITT)

Each subject who participated in a CHIVITT cohort will be contacted approximately 4 weeks (allowable window is 3-5 weeks) from their discharge from a CHIVITT cohort. The participant will be asked whether they have fully recovered from their influenza illness (if any) and whether there were any interim unscheduled medical visits. Venous whole blood (~10 mL) will be collected. Nasal wash specimen (~5-10 mL) will be collected. The participant will be afforded the ability to ask questions or raise concerns and to be provided the answers.

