9 OUTCOMES AND DATA ANALYSIS

9.1 Primary Outcome Measure – Attack Rate of Influenza

The SAR of influenza infection will consist of virological confirmation, symptomatic infection, or serological evidence of an influenza infection.

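### A 4-fold HAI rise alone counts as a secondary infection, and nothing in this protocol separates a rise due to exposure from one due to influenza vaccination or community influenza after discharge

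*Protocol*

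**What the plan says.** Protocol 9.1 states that the SAR "will consist of virological confirmation, symptomatic infection, or serological evidence of an influenza infection". The limbs are joined by *or*, so serology alone is enough. Under 9.1.3, seroconversion is a "4 -fold increase in serum HAI titer from baseline" or more. No sample times, molecular support or attribution condition are attached. A second serological route in 9.1.3, a fixed titre of at least 40, is tied to 1 month after the CHIVITT.

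For the samples:
- Section 8.1.1 lists "Venous whole blood (~10 mL) collection for HAI and FRNT assays" at admission.
- Section 8.1.7 adds a discharge blood. Section 6.9 allows discharge from 2 days after the last exposure event.
- Section 8.1.8 places the next blood "approximately 4 weeks (allowable window is 3-5 weeks) from their discharge from a CHIVITT cohort".

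At that 1-month visit the participant is asked "whether they have fully recovered from their influenza illness (if any) and whether there were any interim unscheduled medical visits". The visit has no vaccine question, no onset date and no respiratory panel. The Recipient criteria in 4.1 do not mention influenza vaccination. Vaccines are part of the history taken at admission (8.1.1), covering 90 days before screening or the time since the last study visit.

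Section 6 says the studies are "anticipated to occur during the peak of local seasonal influenza transmission", and that Recipients are selected partly for low titres to the circulating virus.

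**The concern.** The primary endpoint is meant to measure infection acquired from Donors during controlled exposure. Between the two bloods that the schedule implies, Recipients spend several weeks at home, in or near the influenza season, where they may be vaccinated or infected. Either can raise a low titre 4-fold. Applied as written, 9.1.3 counts both as CHIVITT transmissions.

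The intervention effects on SAR are at stake. So are the infective-dose and susceptibility objectives in section 5, which need each counted infection to come from the measured exposure. A later analysis document could state an attribution rule, but it could not apply one to dates that no visit collects.

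**Working it through.** **Interval.** With a stay of about 14 days and a follow-up window of 21-35 days, the bloods are 14 + 21 = 35 to 14 + 35 = 49 days apart. The share outside quarantine is 21/35 = 60% to 35/49 = 71%. Baseline as the admission sample is an inference. The 1-month sample is the only realistic convalescent one, because the discharge blood can come 2 days after the last exposure.

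**The plan's own figures (9.2).** The inputs are a control SAR of 25%, one-sided alpha of 5%, and 84% power in both cases:
- air hygiene: 79% reduction, 0.25 × 0.21 = 5.25%, 54 in the intervention group;
- shield and hand hygiene: 76% reduction, 0.25 × 0.24 = 6%, 63 in the intervention group.

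The control group size is not stated; I take it as equal. A pooled two-proportion test gives 82.7% (n = 54) and 84.7% (n = 63) two-sided, close to 84%. The stated one-sided test gives 89.8% and 91.1%. Both versions are carried below.

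**Effect of background.** Let b be the share of Recipients not infected in the trial who have a 4-fold rise from another cause. The documents give no value, so a range is shown. The observed rate is q = p + (1 − p)b. For example, at b = 5% the control rate is 0.25 + 0.75 × 0.05 = 0.2875 and the shield rate is 0.06 + 0.94 × 0.05 = 0.107. The observed reduction is 1 − 0.107/0.2875 = 62.8%.

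| b | Control | Shield/hand | Reduction | Power, two-/one-sided (n = 63) | Air hygiene | Reduction | Power, two-/one-sided (n = 54) |
|---|---|---|---|---|---|---|---|
| 0 | 25.0% | 6.0% | 76% | 84.7 / 91.1% | 5.25% | 79% | 82.7 / 89.8% |
| 2% | 26.5% | 7.9% | 70% | 79.8 / 87.7% | 7.1% | 73% | 77.5 / 86.0% |
| 5% | 28.8% | 10.7% | 63% | 72.6 / 82.3% | 10.0% | 65% | 69.9 / 80.1% |
| 10% | 32.5% | 15.4% | 53% | 61.6 / 73.1% | 14.7% | 55% | 58.7 / 70.6% |

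The dilution is sizeable because few true events are expected under intervention. With 63 Recipients at 6%, 3.8 true infections are expected; b = 5% adds 63 × 0.94 × 0.05 = 3.0 others. That is 44% of that arm's cases, against 0.0375/0.2875 = 13% in controls.

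**Why the air-hygiene columns are only conditional.** They assume parallel groups with equal b. Section 6.1 intends Year 1 as low air hygiene only, with alternation within cohorts in later years, so b may differ by year. Two extremes, in which the two conditions fall wholly in different years, show that the direction is open:
- b = 5% under low air hygiene only: 1 − 0.0525/0.2875 = 82%, above the true 79%;
- b = 5% under high air hygiene only: 1 − 0.0999/0.25 = 60%.

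The actual mix of years would fall inside such extremes. Where conditions alternate within a cohort, a serology-only event also has no onset date with which to assign it to a condition.

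**The case against.** Much can be said for the plan, and part of it stands.

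- **The size is assumed.** This stands. The documents give no vaccination rate or community attack rate. On the stated one-sided test, power at b = 2% is still 86.0% and 87.7%, above the planned 84%.
- **Time outside quarantine is not time at risk.** This stands. A vaccination or infection shortly before the second blood would not yet raise the titre, and section 6 places the CHIVITT itself, not the following weeks, at the seasonal peak. The 60-71% is an upper description of the window.
- **Partial safeguards exist.** Solicited symptoms run to 7 days after last exposure, which is at most 7 − 2 = 5 days beyond the earliest discharge. Adverse events are collected at follow-up with onset dates, but 7.1 exempts mild to moderate influenza signs for 7 days from onset. The home test in 6.9 is optional and has no attribution rule. Strain-specific titres in 8.2 are described for determining immunity. Daily swabs with batched RT-PCR can identify serology-only cases but cannot say where such a case was acquired.
- **The separate Recipient protocol is not shown** and might restrict vaccination. This protocol cites no such restriction.

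A reader might infer that the trial could report a spurious effect, or that both effects are certainly pulled towards zero. Neither follows. Equal background creates no effect where there is none, which covers the randomized shield comparison; for air hygiene the direction is unknown.

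A reader might also reach for a blunt rule: discard every serology-only case with any vaccine in the recorded look-back, or with onset more than 24-48 hours after last exposure. The look-back is anchored to screening, which can long precede admission, so such a vaccine response may already be in the admission titre. The short cut-off would drop the late-onset infections that 6.9 wants caught.

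**Conclusion.** The point holds in a limited form. As written, 9.1.3 leaves both seroconversion samples unnamed and, on the only realistic reading of the schedule, counts vaccine responses and post-discharge community infections as primary events. For the randomized face-shield and hand-hygiene comparison the expected consequence is dilution: 76% appears as 70%, 63% or 53% at b = 2%, 5% or 10%. At b = 5%, power falls by about 9 points (one-sided) to 12 points (two-sided). For air hygiene, 79% would appear as 73%, 65% or 55% only if background were equal across conditions, which the Year 1 design does not assure.

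These sizes rest on an assumed b, on equal group sizes, and on admission serum as baseline. The defect itself rests on none of the values of b: the rule and the missing dates are in the text.

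**What to change.** 1. In 9.1.3, name the admission serum as baseline and the 1-month serum as the end sample for seroconversion.
2. At the 8.1.8 visit, record the date of any influenza vaccine since admission, and the date of any respiratory illness or positive influenza test since discharge. Use the vaccine history already taken at admission to flag vaccination shortly before entry.
3. Define a serology-only rise as one with no positive molecular test, including batched RT-PCR of the quarantine swabs. Do not count it as a primary SAR event in either of two cases: influenza vaccine was given between the two bloods, or so shortly before admission that the titre could still be rising; or influenza illness or a positive test began after discharge and later than a prespecified window from last exposure. Set that window by reconciling the 24-48 hour incubation in 2.5.1 with the late-onset cases in 6.9. Apply the rule to the fixed-titre route as well, or the same Recipient could return through it.
4. Report the SAR with and without serology-only cases.

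The cost is a few follow-up questions and a short addition to 9.1.3. A few true serology-only transmissions may be lost, and symptomless community infection is not fully removed.
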